6.2 Safety Pausing Rules

The principal investigator and/or local medical monitor will pause administration of Study Drug in the trial if:

1. It is determined that a SUSAR occurred

OR

2. It is determined that a serious adverse event OR an adverse event pattern of grave concern occurred AND is judged to be POSSIBLY, PROBABLY or DEFINITELY related to Study Drug.

If the principal investigator and/or local medical monitor pauses administration of Study Drug in the study, he or she will record this in a memorandum to the study file and notify the sponsor who will then convene the DSMB. If additional clinical information becomes available during this pausing process that reduces the principal investigator's or local medical monitor's assessment of causality, severity or toxicity grade such that study pausing is no longer required by pausing rules, in other word if the PI or medical monitor recognizes their pausing of the study was in error, then the principal investigator, with the agreement of the medical monitor, and DSMB chairman/chairwoman may resume Study Drug administration, record this in a memorandum to the study file, and notify the sponsor.

Since the global medical monitor is unblinded and reviews data from all the sponsor's trials, he or she may become aware of an adverse event pattern of concern not appreciated by the principal investigator or local medical monitor. If the global medical monitor independently determines that an adverse event pattern of grave concern that is judged to be POSSIBLY, PROBABLY or DEFINITELY related to Study Drug has occurred, the global medical monitor will pause administration of Study Drug in the trial, record the study pause in a memorandum to the study file, and notify the local medical monitor, principal investigator and sponsor who will convene the DSMB.

6.3 Safety Stopping Rules

The DSMB must make a determination of relationship of death (or other below) to the Study Drug before determining a need for unblinding to discover if the subject was a SYN023 recipient. The rules for stopping further enrollment and Study Drug administration by the DSMB are below:

- Death in any subject unless the DSMB determines it is UNRELATED to a SYN023 adverse event.
- A life-threatening adverse event in any subject unless the DSMB determines it is UNRELATED to SYN023

- A pattern of significant symptoms, physical findings or laboratory abnormalities (adverse events) that, although individually minor, collectively represent a grave safety concern in the opinion of the investigator or the medical monitor and are judged by the DSMB to be DEFINITELY, PROBABLY or POSSIBLY related to SYN023

The DSMB may recommend resumption of Study Drug administration if the study pause was for reasons less severe than those in the DSMB stopping rules. The DSMB may recommend resumption of enrollment if it judges that changes to the study protocol will eliminate or greatly reduce the safety risks specified in the stopping rules. In the absence of study protocol changes the DSMB must follow the study safety stopping rules.

If a decision to resume study enrollment and Study Drug administration is made the DSMB will record their judgment in a memorandum to the study file and notify the sponsor. The DSMB memorandum will be forwarded to the medical monitors and principal investigators. The clinical site will be allowed to resume activities upon receipt of written notification from the sponsor.

The appropriate regulatory authority will be informed in writing when:

1. The study is stopped
2. The decision is made by the DSMB to discontinue study activities

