5.1.5.5 DSMB Management of Safety Issues in the Trial

If Study Drug administration is paused (see safety pausing rules in Section 6.1) by the principal investigator, the local medical monitor, or the global medical monitor, the DSMB will be convened. The DSMB may review an individual SAE or it may choose to review adverse events, serious adverse events, solicited adverse events, and laboratory and vital signs data. The DSMB may request unblinding any amount of safety information needed to conduct its safety assessment. Only the DSMB and the independent statistician responsible for preparing these analyses would be unblinded during these reviews. All procedures associated with this review, including objectives, data handling, and elements to be included for review will be documented in DSMB minutes.

Based on its review and the protocol stopping rules (Section 6) the DSMB will make recommendations in the DSMB minutes to the sponsor regarding further conduct of the study, changes to the study protocol and further administration of Study Drugs. The conclusions of the DSMB will be communicated to the investigators and the Institutional Review Boards/Ethics Committees and the national regulatory authority. The sponsor agrees to abide by the decision of its DSMB and any directives issued by the national regulatory authority, the Institutional Review Board or Ethics Committee.

If Study Drug administration is paused by the medical monitor or the global medical monitor, the DSMB will be convened. Based on its review and the protocol stopping rules (Section 6) the DSMB will make recommendations in the DSMB minutes to the sponsor regarding further conduct of the study and further administration of Study Drug. The DSMB may review an individual SAE or it may choose to review adverse events, serious adverse events, solicited adverse events, and laboratory and vital signs data. The DSMB may unblind any amount of safety information needed to conduct their assessment. All procedures associated with this review, including objectives, data handling, and elements to be included for review will be documented in DSMB minutes. The conclusions of the DSMB will be communicated to the investigators and the IRB/Ethical Committees and the national regulatory authorities. The

sponsor agrees to abide by the decision of its DSMB and any directives issued by the national regulatory authorities, the Institutional Review Boards or Ethics Committees.

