5.11 Reporting of Serious Adverse Events

Serious adverse events, which include SUSARs, are reported to the sponsor and to the pharmacovigilance (PVG) for the entire study period (see protocol appendix A).

Pharmacovigilance (PVG), PPD Global Ltd.
24 Hour Safety [contact]
24 Hour Safety Hotline [contact]
[contact]

SUSARs are reported even after the trial is over, if the sponsor, local medical monitor or principal investigator becomes aware of them. The site will be provided with specific reporting procedures including the Adverse Event CRF and any supplemental reporting forms to be used. Serious adverse events will be reported on the Adverse Event CRF using a recognized medical term or diagnosis that accurately reflects the event.

Serious adverse events will be assessed by the investigator and the local medical monitor according to their roles (as described in Sections 5.1.1 and 5.1.3) for severity, causal relationship

to the Study Drug, and expectedness. The onset and resolution dates of the event and the action taken in response to the event will be documented. If the event has not resolved by the final study visit, it will be documented as “ongoing” on the CRF, however, follow-up of the SAE must continue until resolved. Information recorded on the CRF must be substantiated in the source documents.

The SAE Report form completed for that event must be faxed by the principal investigator or his/her designee, within 24 hours (one calendar day) of the clinical site becoming aware of the event, to the local medical monitor and to the Pharmacovigilance (PVG) at PPD (Appendix A). The AE CRF should be completed with all information known at the time; the Supplemental SAE Report (paper form) should be completed and both forms faxed (even if all information concerning the event is not yet known) within the first 24 hours of awareness of the event.

Fatal or life-threatening serious adverse events that the investigator suspects are related to the Study Drug should be telephoned to the local medical monitor immediately upon the investigator's awareness of the event. If the local medical monitor is required by the protocol or chooses to suspend enrollment s/he shall immediately create a written memorandum for record to the study file and telephonically notify the sponsor of this act.

Contact information for all safety personnel are contained in the Team Contact List which will be stored on site in the Site Regulatory Binder and maintained by the study sponsor.

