Investigators must not wait to collect additional information to fully document the event before notifying the local medical monitor and pharmacovigilance (PVG) of a serious adverse event. The initial notification should include the following (at minimum):

- Protocol number and name and contact number of the investigator
- Subject ID number (and initials and date of birth, if available)
- Date subject received Study Drug
- Serious adverse event(s) and date of event onset
- Current status of subject

The sponsor has authorized the PPD to be the pharmacovigilance (PVG) to execute its responsibilities for safety report submission to the appropriate regulatory authorities within specific time periods of being notified of the event (within 7 or 15 calendar days depending the character of the SUSAR); therefore, it is important that the investigator submit additional information requested as soon as it becomes available.

The sponsor will notify the DSMB of all SUSARs within 3 working days of becoming aware of an event and will provide all follow-up information in a timely manner.

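### Section 6.3 needs a DSMB decision on every death or life-threatening event, but no prompt route brings one to the DSMB when both blinded raters call it unrelated

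*Protocol*

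**What the plan says.** Protocol Section 6.3 lists the rules under which the DSMB stops further enrollment and dosing. The first is "Death in any subject unless the DSMB determines it is UNRELATED to a SYN023 adverse event" and the second is "A life-threatening adverse event in any subject unless the DSMB determines it is UNRELATED to SYN023". The same section requires the DSMB to rule on relationship before it considers unblinding. Unless the protocol is changed, the DSMB is bound by these rules.

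Section 5.11 sets out who is told of an event:

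- The SAE form goes within 24 hours "to the local medical monitor and to the Pharmacovigilance (PVG) at PPD". The DSMB is not named.
- An immediate telephone call to the local medical monitor depends on suspected causality: "Fatal or life-threatening serious adverse events that the investigator suspects are related to the Study Drug should be telephoned".
- The one event-level notice to the DSMB is "The sponsor will notify the DSMB of all SUSARs within 3 working days of becoming aware of an event".

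Section 6.2 requires the investigator or local medical monitor to pause dosing for a SUSAR. They must also pause for an SAE, or a grave pattern of adverse events, that "occurred AND is judged to be POSSIBLY, PROBABLY or DEFINITELY related to Study Drug". The sponsor then convenes the DSMB, and Section 5.1.5.5 repeats the link: "If Study Drug administration is paused by the medical monitor or the global medical monitor, the DSMB will be convened".

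**The concern.** Section 6.3 places the causality decision on deaths and life-threatening events with the DSMB, which can unblind. The general routes by which such an event would reach the DSMB as it occurs all start from a causality rating already made by people who are blinded. An event they rate unrelated is screened out of those routes, although Section 6.3 reserves that judgement to the DSMB.

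The consequence would be continued enrollment and dosing after a death or life-threatening event on which the DSMB has not ruled and of which it may not yet know. The same rule governs all three dosing phases (initial LRG, general LRG and NRG).

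**Working it through.** No design figure is in dispute, so the check traces one event through the text and then counts what the scheduled reviews cover.

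**One event, step by step.** Take a death that the investigator and the local medical monitor both rate unlikely related.

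1. *Who rates it.* Sections 5.1.1 and 5.1.3 say both are blinded. Under Section 5.5 the higher of the two ratings prevails, and unlikely related counts as unrelated. Both must therefore choose one of the two lowest categories for the event to be classed as unrelated.
2. *Is it a SUSAR?* Section 5.10 requires the event to be related, serious and unexpected. It is not related, so the 3-working-day notice does not apply.
3. *Does it force a pause?* Section 6.2 needs a SUSAR or a rating of at least possible. It has neither, so no mandatory pause follows and the DSMB is not convened by that route.
4. *Does the SAE form reach the DSMB?* Section 5.11 names only the local medical monitor and pharmacovigilance.
5. *What does Section 6.3 require?* A DSMB determination, failing which the event is a stop.

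Steps 2 to 4 supply no event-level input to step 5. A serious event rated possible or higher does reach the DSMB, through the Section 6.2 pause, even if it is expected. The gap is confined to events that both raters call unrelated.

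**A contrast within the protocol.** Section 6.1.2 pauses dosing for DSMB review of any clinically suspected or laboratory-confirmed rabies case, with no causality condition. Section 6.3 has no matching trigger for deaths or life-threatening events.

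**Scheduled reviews.**

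| Review | Data | Position relative to dosing |
|---|---|---|
| Initial LRG (5.1.5.2) | 20 subjects, through Study Day 29 | After all 20 are dosed |
| Whole LRG (5.1.5.3) | 80 subjects, through Study Day 99 | After all 80 are dosed, before the NRG |
| NRG (5.1.5.4) | When 80 subjects have completed Study Day 99 | During NRG enrollment |
| NRG progress (2.2.7) | Safety and pharmacodynamics | No date or frequency given |

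From the enrollment figures in Protocol Section 2.3:

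- Subjects with a dated review through Study Day 99: 80 + 80 = 160 of 448.
- NRG subjects without one: 368 − 80 = 288.
- Subject-days under a dated review: at least 160 × 99 = 15,840, out of 448 × 365 = 163,520 planned, or about 10%.

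The last figure is a floor on coverage and is not a measure of risk. Later NRG subjects may contribute partial data to the 80-subject review.

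**Timing of the NRG review.** The documents give no accrual period. Assume uniform NRG accrual over 6 to 12 months (182.5 to 365 days), with subjects completing in order of enrollment. Study Day 99 falls 98 days after Study Day 1, so the number dosed when the 80th subject completes it is 80 + 98 × (368 / accrual days).

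- 12 months: 80 + 98 × 1.008 = 179 dosed, 189 still to come.
- 6 months: 80 + 98 × 2.016 = 278 dosed, 90 still to come.

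On that assumption the only dated NRG review falls after 179 to 278 of the 368 have been dosed, and no dated review covers the remaining 90 to 189.

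**The case against.** A reader might infer that the DSMB learns of nothing but SUSARs, meets only after a pause based on relatedness, and would never see an event rated unrelated. The documents do not support that, for these reasons:

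- Both LRG reviews supply adverse events with no causality filter, and both make advancement conditional on no Section 6.3 rule having been met. The DSMB must therefore check deaths against that rule before each step.
- Section 5.1.5.4 adds the NRG review, and Section 2.2.7 describes oversight during the NRG period.
- Under Section 5.1.4 the global medical monitor may unblind selected SAEs and have the DSMB convened over a suspected pattern without a pause. That section describes the DSMB as the body that ordinarily reviews unblinded SAEs.
- Suspected rabies always goes to the DSMB, and Section 5.1.1 lets the investigator pause the trial on suspicion of significant risk.

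The charter is a further objection. Section 5.1.5 says the DSMB operates under it, SAP Section 13 refers DSMB summaries to it, and it may set meeting frequency or event notices.

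All of this stands, and it limits the point to prompt, event-level reporting. It does not close the gap. The LRG reviews come after everyone in the phase is dosed. The global monitor's route is discretionary and depends on a pattern. The investigator's discretionary pause needs a suspicion that an unrelated rating implies is absent. The charter governs how the DSMB works, whereas the sponsor's duty to notify is written in the protocol, and it names SUSARs.

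A reader might also see Sections 6.2 and 6.3 as contradicting each other on who decides. They are two tiers: pausing by the investigator and monitors, and stopping by the DSMB. They are mismatched because the first does not feed the second all the events on which the second must rule.

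**Conclusion.** The concern holds in a limited form. Section 6.3 requires a DSMB determination on deaths and life-threatening adverse events. The protocol has no prompt, event-level route that brings one to the DSMB when both blinded raters call it unrelated. The DSMB may then see it only at a scheduled review, and no dated review follows the 80-subject NRG review.

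The size rests on the protocol's own counts: 288 of 368 NRG subjects lie outside any dated review through Study Day 99. The finding that 179 to 278 are dosed before that review depends on the assumed 6 to 12 month accrual. The conclusion also assumes that the charter adds no event notice, which could not be checked.

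Two further inferences are not supported:

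- *That the trial would be in breach at the first such death.* Section 6.3 sets no time limit for the DSMB's determination.
- *That such a death is probable.* The documents give no background death rate and no share of deaths likely to be rated unrelated. A figure based on the full 365-day follow-up would also count deaths after the last dose, when Section 6.3 has no enrollment or dosing left to stop. The point does not need a probability, because a single event would expose the gap.

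**What to change.** Reconcile Protocol Sections 5.1.5.5, 5.11, 6.2 and 6.3, and check the result against the DSMB charter.

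- In Section 5.11, widen the sponsor's DSMB notice beyond SUSARs to the events on which Section 6.3 requires a DSMB determination: deaths and life-threatening adverse events, regardless of the blinded causality rating. The existing 24-hour SAE report and 3-working-day clock can carry it.
- Make Sections 5.1.5.5 and 6.3 refer to that notice, so that the path from event to determination is written down.
- The sponsor must also reconcile Sections 6.2 and 6.3 on what happens to dosing while the DSMB decides. No clinical or stopping rule is proposed here.
- In the same revision, settle two related inconsistencies. The DSMB's list of duties in Section 5.1.5 places the 80-subject review at Study Day 9, while Section 5.1.5.4 says Study Day 99. Section 5.1.5.5 cites Section 6.1 for the safety pausing rules, which are in Section 6.2.

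The cost is protocol wording and a few more DSMB notices. Sample size, analysis and data collection are unaffected.

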7 STATISTICAL CONSIDERATIONS

The planned statistical analyses for this study are outlined below. A detailed statistical analysis plan will be created and finalized prior to database lock and preparation of any unblinded preliminary data review and for preparation of the final study report (see Section 7.9).

7.1 Subject Populations

As-Treated Population (Safety Population)

Since post-exposure treatment of rabies is urgent and should not be delayed, randomization and prophylaxis will begin after a screening event that includes informed consent, urine pregnancy test and survey of inclusion criteria before some exclusion criteria have been confirmed. High-risk rabies exposure victims that meet all initially knowable inclusion/exclusion criteria will be randomized receive Study Drug and begin a regimen of rabies vaccination. All subjects who are randomized and receive Study Drug are included in the “as-treated” population.

LRG Per-Protocol Population (Initial Enrollment)

The LRG initial enrollment group is described in all subjects who

- 1) are randomized as part of the initial enrollment group
- 2) receive the correct Study Drug

- 3) have inclusion/exclusion criteria confirmed
- 4) complete the rabies vaccinations schedule by Study Day 29
- 6) lack major protocol deviations
- 7) have adequate wound treatment and Study Drug injection of all exposure sites

will be included in the “per-protocol” population. Exclusion criteria that must be confirmed are the species of the biting animal; a high risk exposure (WHO Category 3); interval \leq 54 hours from the bite to the start of prophylaxis; the absence of RVNA \geq 0.1 IU in serum obtained at Study Day 1, time “0” blood collection (WHO, 2013). Subjects who are discovered to not have satisfied criteria for the per-protocol population may be excluded from that population by the Per-protocol Adjudication Board.

LRG Per-Protocol Population (General Enrollment)

All subjects who

- 1) are randomized as part of the LRG general enrollment
- 2) receive the correct Study Drug
- 3) have inclusion/exclusion criteria confirmed
- 4) complete the rabies vaccinations schedule by Study Day 29
- 6) lack major protocol deviations
- 7) have adequate wound treatment and Study Drug injection of all exposure sites

will be included in the “per-protocol” population. Exclusion criteria that must be confirmed are the species of the biting animal; a high risk exposure (WHO Category 3); interval \leq 54 hours from the bite to the start of prophylaxis; the absence of RVNA \geq 0.1 IU in serum obtained at Study Day 1, time “0” blood collection (WHO, 2013). Subjects who are discovered to not have satisfied criteria for the per-protocol population may be excluded from that population by the Per-protocol Adjudication Board.

NRG Per-Protocol Population

All subjects who

- 1) are randomized to the NRG
- 2) receive the correct Study Drug
- 3) have inclusion/exclusion criteria confirmed
- 4) complete the rabies vaccinations schedule by Study Day 29
- 6) lack major protocol deviations
- 7) have adequate wound treatment and Study Drug injection of all exposure sites
- 8) are not part of the LRG enrollment

will be included in the “per-protocol” population. Initial exclusion criteria that must be confirmed are the nature of the exposure including the species of the animal; a high risk exposure (WHO Category 3); interval \leq 54 hours from the bite to the start of prophylaxis; the absence of RVNA \geq 0.1 IU in serum obtained at Study Day 1, time “0” blood collection (WHO, 2013).

Subjects who are discovered to not have satisfied criteria for the per-protocol population may be excluded from that population by the Per-protocol Adjudication Board.

7.2 Demographics and Protocol Compliance

Demographic parameters (age, gender, and race/ethnicity) and other baseline characteristics will be summarized by treatment group for all subjects in the safety population.

Subject enrollment to each study group will be conducted based on timing of completion of study eligibility requirements. Randomization will be adjusted by the randomization center to maintain stratification and site allocation. Any resulting imbalance in baseline characteristics between study groups will be examined.

Listings of randomized subjects who missed any dose of Study Drug or rabies vaccine and of subjects with protocol deviations (to be defined in the statistical analysis plan) will be provided.

7.3 Primary Objective: Efficacy Analyses

The primary objective is a composite endpoint with four elements in three areas:

- the geometric mean RVNA concentration for SYN023 recipients is superior to the geometric mean RVNA concentration for HRIG recipients on Study Day 8
- the immune response to rabies vaccine on Study Day 99: RVNA GMT noninferiority SYN023 vs HRIG
- the response to rabies vaccine on Study Day 99: $RVNA \geq 0.5 \text{ IU/mL}$ % noninferiority SYN023 vs HRIG
- the absence of clinical rabies.

A similar analyses will be performed for both the per-protocol and the as-treated population for sensitivity analysis.

- The first element is superiority of the geometric mean SYN023 on study Day 8 in serum. RVNA was selected because it is a generally accepted surrogate for rabies vaccine protection. Animal and human studies suggest that tissue levels of RVNA may correlate with protection by neutralizing the rabies virus before the virus is taken up into peripheral nerves from where it gains fatal access to the central nervous system even in the presence of neutralizing antibodies (Watson et al. 1981, Schumacher et al. 1989, Shankar et al. 1991). It is logical that serum levels represent passive diffusion along a concentration gradient from sites of local infiltration. Tissue RVNA concentrations are likely higher than serum RVNA concentrations. The reason for HRIG injection in addition to vaccination is to provide immediate rabies neutralizing antibodies in tissues to prevent the entry of rabies virus into nervous tissue before rabies vaccination has elicited neutralizing antibodies. This practice in historical studies seems to have reduced infection from rabies compared to rabies exposed individuals receiving only vaccination.

If it is possible to demonstrate quicker and higher concentrations in the blood of RVNA from SYN023 then this may be evidence of greater potency and perhaps effectiveness.

The pharmacodynamic variable Synermore selected to assess the prompt availability of RVNA is the area under the curve for serum RVNA concentration (Synermore's correlate of effectiveness) from Study Day 1 through Study Day 15 when vaccine antibodies will have begun to predominate. Synermore will demonstrate superiority of the AUEC₁₋₈ with an 80% power of observing a 10% margin of superiority with a p value ≤ 0.025 .

- The second element is immune response to the rabies vaccine on Study Day 99 measured by the noninferiority of the Study Day 99 geometric mean concentrations of RVNA in SYN023 recipients compared to Study Day 99 geometric mean concentrations of RVNA in the HRIG recipients. It is important that any immunoglobulin product administered be compatible with rabies vaccination and not significantly inhibit the immune response to rabies vaccination. When should this comparison of immunogenicity be performed and secondly what margin of non-inferiority should be employed? It is Synermore's position that assessment of rabies vaccine immunogenicity should be performed on or around Study Day 99. This interval is over four half-lives of human IgG. Anti-rabies antibodies administered for prophylaxis will have largely dissipated and Study Day 99 GMC RVNA values will reflect the long term immunogenicity of rabies vaccination. Synermore defines non-inferiority rabies vaccine response of the as a 20% margin of non-inferiority and equal allowance (number of subjects in SYN023 = number of subjects in HRIG) and alpha is taken to be ≤ 0.025 .
- The third element is immune response to the rabies vaccine on Study Day 99 measured by the noninferiority percent of the study population RVNA ≥ 0.5 IU/mL SYN023 vs HRIG. This approach assesses the noninferiority of the percent of subjects who have a serum RVNA concentration that is generally recognized as protective, the more important measure of vaccine compatibility.
- The fourth element is the absence of probable or confirmed cases of clinical rabies in the SYN023 recipients (Section 3.9.1). There is no need to specify "suspected" cases of rabies since entry into the protocol requires exposure to a possibly rabid animal and this is the factor that makes a case "probable" as opposed to "suspected." It is likely that there will no cases of rabies in the per protocol population of either treatment arm therefore a non-inferiority test could not be done. Synermore estimates the failure rate of properly administered PEP in adults to be between 1 in 1000 and 1 in 10,000 (Hemachudha et al. 1999, Hampson et al. 2008, Quiambao et al. 2008, Quiambao et al. 2009 Shantavasinkul et al. 2010, Wilde et al. 2007). A single case of rabies in a subject properly treated with PEP meeting the per-protocol conditions in a 160 subject sample of adults would be an occurrence rate of 0.63% and the 95% confidence interval extends from 0 to 2%. This rate of failure would be evidence for a lack of effectiveness.

7.4 Secondary Objectives: Clinical and Pharmacodynamic Efficacy.

To demonstrate that the proportion of SYN023 recipients with blood RVNA concentrations that meet the generally accepted as adequate threshold ≥ 0.5 IU/mL, for Study Days 8-99 in the per-protocol population is not inferior to the same proportion in HRIG recipients. A similar analysis will be performed for the as-treated population for sensitivity analysis.

To demonstrate that SYN023 administered within 54 hours of rabies exposure with rabies vaccinations prevents all probable or confirmed clinical rabies cases.

To describe the ratio of the geometric mean concentrations of RVNA at each time point in SYN023 recipients divided by the geometric mean concentrations of RVNA in HRIG recipients for the per-protocol and as-treated populations for each risk group.

To describe ant effect of increasing BMI on RVNA concentrations.

